### **17.3.1 Informed Consent Form**

Informed consent will be obtained in accordance with the Declaration of Helsinki, ICH GCP, US Code of Federal Regulations for Protection of Human Subjects (21 CFR 50.25[a,b], CFR 50.27, and CFR Part 56, Subpart A), the Health Insurance Portability and Accountability Act (HIPAA, if applicable), and local regulations.

The Sponsor's Sample Informed Consent Form (ICF) will be provided to each site. Sponsor or its designee must review and approve any proposed deviations from the Sample ICF or any alternate consent forms proposed by the site before IRB submission. Patients must be re-consented to the most current version of the Consent forms during their participation in the study. The final IRB-approved Consent Forms must be provided to Sponsor for regulatory purposes.

The Consent Forms must be signed by the patient before her participation in the study. The case history for each patient shall document the informed consent process and that written informed consent was obtained prior to participation in the study. A copy of each signed Consent Form must be provided to the patient. If applicable, it will be provided in a certified translation of the local language.

All signed and dated Consent Forms must remain in each patient's study file and must be available for verification by study monitors at any time.

The Informed Consent Form should be revised whenever there are changes to procedures outlined in the informed consent or when new information becomes available that may affect the willingness of the patient to participate.

For any updated or revised Consent Forms, the case history for each patient shall document the informed consent process and that written informed consent was obtained for the updated/revised Consent Form for continued participation in the study. The final revised IRB-approved Informed Consent Form must be provided to Sponsor for regulatory purposes.

## **17.4 REPORTING OF SAFETY ISSUES AND SERIOUS BREACHES OF THE PROTOCOL OR ICH GCP**

In the event of any prohibition or restriction imposed (i.e., clinical hold) by an applicable Competent Authority in any area of the world or if the Investigator is aware of any new information which might influence the evaluation of the benefits and risks of the investigational product, the Sponsor should be informed immediately.

In addition, the Investigator will inform the Sponsor immediately of any urgent safety measures taken by the Investigator to protect the study subjects against any immediate hazard and of any serious breaches of this protocol or of ICH GCP that the Investigator becomes aware of.

## **17.5 SPONSOR DISCONTINUATION CRITERIA**

Premature termination of this study may occur because of a regulatory authority decision, change in opinion of the IRB, drug safety problems, or at the discretion of the Sponsor. In addition, the Sponsor retains the right to discontinue development of GDC-0810 at any time.

If a study is prematurely terminated or discontinued, the Sponsor will promptly notify the Investigator. After notification, the Investigator must notify the respective IRB and contact all participating subjects and the hospital pharmacy (if applicable) within a 4-week time period. As directed by the Sponsor, all study materials must be collected and all CRFs completed to the greatest extent possible.

## **17.6 PUBLICATIONS**

Regardless of the outcome of a trial, the Sponsor is dedicated to openly providing information on the trial to healthcare professionals and to the public, both at scientific congresses and in peer-reviewed journals. The Sponsor will comply with all requirements for publication of study results. For more information, refer to the Roche Global Policy on Sharing of Clinical Trials Data at the following Web site:

*[www.roche.com/roche\\_global\\_policy\\_on\\_sharing\\_of\\_clinical\\_study\\_information.pdf](http://www.roche.com/roche_global_policy_on_sharing_of_clinical_study_information.pdf)*

The results of this study may be published or presented at scientific congresses. For all clinical trials in patients involving an IMP for which a marketing authorization application has been filed or approved in any country, the Sponsor aims to submit a journal manuscript reporting primary clinical trial results within 6 months after the availability of the respective clinical study report. In addition, for all clinical trials in patients involving an IMP for which a marketing authorization application has been filed or approved in any country, the Sponsor aims to publish results from analyses of additional endpoints and exploratory data that are clinically meaningful and statistically sound.

The investigator must agree to submit all manuscripts or abstracts to the Sponsor prior to submission for publication or presentation. This allows the Sponsor to protect

proprietary information and to provide comments based on information from other studies that may not yet be available to the investigator.

In accordance with standard editorial and ethical practice, the Sponsor will generally support publication of multicenter trials only in their entirety and not as individual center data. In this case, a coordinating investigator will be designated by mutual agreement.

Authorship will be determined by mutual agreement and in line with International Committee of Medical Journal Editors authorship requirements. Any formal publication of the study in which contribution of Sponsor personnel exceeded that of conventional monitoring will be considered as a joint publication by the investigator and the appropriate Sponsor personnel.

Any inventions and resulting patents, improvements, and/or know-how originating from the use of data from this study will become and remain the exclusive and unburdened property of the Sponsor, except where agreed otherwise.

**Appendix 1 Schedule of Activities: Phase Ia**

	Screening	PK Week Lead-In	Cycle 1				Cycle 2+ [1]	End of Treatment [2]	Safety Follow-Up (+ 2 days) [3]
Protocol Activities	≤ 28 days of 1 st dose	Day -7	Day 1	Day 8 (± 1 day)	Day 15 (± 1 day)	Day 22 (± 1 day)	Labs CT/MRI scans		
Baseline Documentation									
Informed Consent	X								
Medical/Oncological History [4]	X								
Physical Examination [5]	X	X	X	X	X	X	X	X	(X)
CT/MRI Brain [6]	X								
Laboratory Studies									
Hematology and Blood Chemistry [7]	X	X	X	X	X	X	X [1]	X	(X)
Urinalysis [7]	X						X	X	
Circulating Tumor DNA [7]	X								X
Trough PK Sample [8]		X		X	X	X			
GDC-0810 Dosing [9]		X	X→	→	→	→	→		
12-Lead ECG [10]	X						C2D1 (at 2 hours postdose)		
24-hr PK Assessment [11]		X [12]					C2D1 and C2D2		
Efficacy/PD Assessments									
CT/MRI Chest, Abdomen, Pelvis [13]	X						X		
Bone Scan [13]	X						X		
FES-PET/CT Scan; collect PK, E2 and SHBG samples prior to performing the scan [14]	X						C2D3; C3 if needed		
Tumor Biopsy (optional) [15]	X						C2D8 (± 1 day)		
Other Clinical Assessments									
ECOG and Vital Signs	X	X	X	X	X	X	X	X	(X)
Adverse Events/Con Meds and Treatments [16]	X	X	X	X	X	X	X	X	X

## Appendix 1 Schedule of Activities: Phase Ia (cont.)

Protocol Activities	Screening	PK Week Lead-In	Cycle 1				Cycle 2+ [1]	End of Treatment [1]	Safety Follow-Up (+ 2 days) [2]
	≤ 28 days of 1 st dose	Day -7	Day 1	Day 8 (± 1 day)	Day 15 (± 1 day)	Day 22 (± 1 day)	Labs CT/MRI scans		
Transvaginal Ultrasound [17]	X						X	X	
Study Drug Compliance [18]				X	X	X	X	X	

Study assessments may be delayed or moved ahead of the window specified to accommodate holidays, vacations, and unforeseen delays.

### Footnotes

1. Cycle 2+: To be performed per institutional guidelines and/or as clinically indicated except for ECOG, physical examination, vital signs, creatinine, liver function tests, adverse events, concomitant medication, and study drug compliance should be monitored at each cycle.
2. End of Treatment: These assessments do not need to be completed if they have been performed within 1 week of study withdrawal (within 4 weeks for imaging studies and 3 months for the transvaginal ultrasound).
3. Safety Follow-Up: Patients should be evaluated for safety up to 28 days after the last dose of study treatment. Physical examination (including ECOG and vitals), hematology, and blood chemistry should be performed as clinically indicated. Adverse events should be followed until all serious or study drug-related toxicities have resolved or are determined to be “chronic” or “stable”, whichever is later.
4. Medical/Oncological History: Includes oncologic history, demographics, history of other disease processes (active or resolved) and concomitant illnesses.
5. Physical Examination: Examination of major body systems, including known and suspected sites of disease. Height should be collected at Screening.
6. CT/MRI of the brain: To be performed as needed to rule out the presence of untreated CNS metastases.
7. Samples for hematology, blood chemistry (except creatinine and liver function tests), and urinalysis will be performed per institutional guidelines and as clinically indicated. Circulating tumor DNA will be analyzed by a specialty laboratory. Creatinine and liver function tests should be monitored at each cycle. ctDNA will be collected at screening and end of study visit.
8. Trough PK Sample: Samples should be obtained predose on the specified days ( patient should not take the study drug at home ). Additionally, if clinically feasible, samples should be obtained at the time of any serious and/or unusual adverse events that may be causally related to study drug.
9. GDC-0810 Dosing: GDC-0810 will be orally self-administered, except on clinic days, when they will take their daily dose at the clinic, prior to any study assessment. One cycle consists of 28 days.
10. ECG: Single 12-lead ECGs will be collected at Screening and at Cycle 2 Day 1 (at the 2-hour postdose timepoint) to assess the QTc interval. If there is QTc interval prolongation (Grade > 1), the ECG should be over read by a cardiologist at the site for confirmation.
11. 24-Hour PK Assessment: Samples will be drawn relative to time of dose at 0 (predose), 0.5, 1, 1.5, 2, 3, 4, 6, 8, and 24 hours postdose.

## Appendix 1 Schedule of Activities: Phase Ia (cont.)

12. Day -7 PK Assessment: Samples will be drawn relative to time of dose at 0 (predose), 0.5, 1, 1.5, 2, 3, 4, 6, 8, 24, and 48 hours postdose.
13. Tumor Imaging: CT scans of the chest, abdomen and pelvis and a bone scan will be performed to assess disease status at Screening, and per institutional guidelines and as clinically indicated.
14. FES-PET/CT scans: Functional ER imaging will be performed at Screening and at Cycle 2 Day 3 (between $\geq 18$ and $\leq 24$ hours post- evening dose from the previous day) starting at Dose Level 2 (200 mg). If needed, a third scan will be performed at Cycle 3 (same day as the tumor evaluation scans, between $\geq 2$ and $\leq 12$ hours postdose). If low FES uptake is observed at Screening, the investigator will determine whether the post-treatment scans are warranted. Blood samples for analysis of drug levels (PK), E2, and SHBG should be collected prior to each PET scan performed.
15. Tumor Biopsies (optional): Pre- and post-treatment biopsies from the same (whenever feasible) soft tissue or visceral metastatic lesion will be collected at Screening and Cycle 2 Day 8, between $\geq 2$ and $\leq 12$ hours postdose.
16. Adverse Events and Concomitant Medications/Treatments: Patients must be followed for adverse events and associated concomitant medications and treatments on a monthly basis, from the first day of study treatment until at least 28 days after the last dose of study treatment, or until all serious or study drug-related toxicities have resolved or are determined to be “chronic” or “stable”, whichever is later.
17. Transvaginal Ultrasound (if applicable): Assessment of endometrial thickness will be performed at Screening, at the end of treatment (if treated for at least 2 cycles), and as clinically indicated. Any abnormal bleeding should be evaluated with a complete gynecological workup.
18. Study Drug Compliance: GDC-0810 bottle(s) including any unused capsules should be brought to each clinic visit for drug accountability.

## Appendix 2 Schedule of Activities: Phase IIa

Protocol Activities	Screening	Cycle 1	Cycles 2+ [1]		End of Treatment [2]	Safety Follow-Up (+ 2 days) [3]
	≤ 28 days of 1 st dose	Day 1	Labs Biopsies, scans			
Baseline Documentation						
Informed Consent	X					
Medical/Oncological History [4]	X					
Physical Examination [5]	X	X	X		X	(X)
CT/MRI Brain [6]	X					
Laboratory Studies						
Hematology and Blood Chemistry [7]	X	X	X [1]		X	(X)
Urinalysis [7]	X		X		X	
Circulating tumor DNA [7]	X		C3 only		X	
Pharmacogenomic sample [7]		X				
Trough PK Sample [8]		X	X (only Cycles 3, 4)			
GDC-0810 Dosing [9]		X→	X→			
Triplet 12-Lead ECG [10]	X		Cycle 2 Day 1 predose and at 1, 2, 3, 4, 6 hours		X	
PK Sample [11]			Cycle 2 Day 1 predose and at 1, 2, 3, 4, 6 hours following dosing			
Efficacy/PD Assessments						
CT/MRI Chest, Abdomen, Pelvis [12]	X		X		X	
Bone Scan [12]	X		X		X	
FES-PET/CT Scan (Cohort A1 patients) Collect E2 and SHBG samples prior to performing the scan [13]	X		C3 and whenever disease progression is suspected			

## Appendix 2 Schedule of Activities: Phase IIa (cont.)

	Screening	Cycle 1	Cycles 2+ [1]	End of Treatment [1]	Safety Follow-Up (+ 2 days) [2]
Protocol Activities	≤ 28 days of 1 st dose	Day 1	Labs Biopsies, scans		
Tumor Biopsy (Cohort A patients, if feasible) [14]	X				
Archival Tissue Sample (optional) [15]	X				
Other Clinical Assessments					
ECOG and Vital Signs	X	X	X	X	(X)
Adverse Events/Con Meds and Treatments [16]	X	X	X	X	X
Transvaginal Ultrasound [17]	X		X	X	
Study Drug Compliance [18]			X	X	

Study assessments may be delayed or moved ahead of the window specified to accommodate holidays, vacations, and unforeseen delays.

### Footnotes

- 1. Cycle 2+:** To be performed per institutional guidelines and/or as clinically indicated except for ECOG, physical examination, vital signs, creatinine, liver function tests, adverse events, concomitant medication, and study drug compliance should be monitored at each cycle.
- 2. End of Treatment:** These assessments do not need to be completed if they have been performed within 1 week of study withdrawal (within 4 weeks for imaging studies and 3 months for the transvaginal ultrasound).
- 3. Safety Follow-Up:** Patients should be evaluated for safety up to 28 days after the last dose of study treatment. Physical examination (including ECOG and vitals), hematology, and blood chemistry should be performed as clinically indicated. Adverse events should be followed up until all serious or study drug-related toxicities have resolved or are determined to be "chronic" or "stable", whichever is later.
- 4. Medical History:** Relevant medical history includes clinically significant diseases; smoking history, use of alcohol and drugs of abuse, including history of current disease, surgeries, other pertinent clinical conditions, and information regarding underlying diseases will be recorded at screening.
- 5. Physical Examination:** Examination of major body systems, including known and suspected sites of disease. Height should be collected at Screening.
- 6. CT/MRI of the brain:** To be performed as needed to rule out the presence of untreated CNS metastases.
- 7. Samples for hematology, blood chemistry (except creatinine and liver function tests), and urinalysis** will be performed per institutional guidelines and as clinically indicated. Circulating tumor DNA will be analyzed by a specialty laboratory. The pharmacogenomic analysis of genes that may affect the PK of GDC-0810 and circulating tumor DNA will be analyzed at specialty laboratories. Creatinine and liver function tests should be monitored at each cycle. ctDNA will be collected at screening, Cycle 3, and end of study visit.
- 8. Trough PK Sample:** Plasma samples should be obtained predose on the specified days (patient should not take the study drug at home). Additionally, if clinically feasible, samples should be obtained at the time of any serious and/or unusual adverse events that may be causally related to study drug.

## Appendix 2 Schedule of Activities: Phase IIa (cont.)

9. GDC-0810 Dosing: GDC-0810 will be orally self-administered within 30 minutes after eating a meal (unless specified otherwise). One cycle consists of 28 days.
10. ECG: Triplicate 12-lead ECGs will be collected approximately 2 minutes apart at Screening, on Cycle 2 Day 1 predose and at 1, 2, 3, 4, and 6 hours following dosing to assess the QTc interval. For real-time safety monitoring of patients, only one ECG printout per timepoint (of the triplicate -matched PK samples) will need to be reviewed by the investigator. For the purposes of central analysis, triplicate ECGs will be obtained in a rigorous and standardized fashion and transmitted digitally to the central reading facility for review and interpretation by specialized cardiac readers. For real-time safety monitoring of patients, only one ECG printout per timepoint (of the triplicate -matched PK samples) will need to be reviewed by the investigator. For the purposes of central analysis, triplicate ECGs will be obtained in a rigorous and standardized fashion and transmitted digitally to the central reading facility for review and interpretation by specialized cardiac readers.
11. PK Sample: PK samples will also be collected predose and at 1, 2, 3, 4, and 6 hours following dosing at Cycle 2 Day 1. If PK sampling times coincide with ECG collection times, the ECGs have to be assessed prior to PK blood collection.
12. Tumor Imaging: CT scans of the chest, abdomen and pelvis and a bone scan will be performed to assess disease status at Screening and per institutional guidelines and as clinically indicated .
13. FES-PET/CT scans: Functional ER imaging will be performed in all Cohort A1 patients at Screening, at Cycle 3 (per Section 11.5.1.2). If low FES uptake is observed at Screening, the investigator will determine whether the post-treatment scan(s) are warranted. Blood samples for analysis of E2 and SHBG should be collected prior to each PET scan performed.
14. Tumor Biopsies: All Cohort A patients with safely accessible soft tissue and/or visceral metastases will have tumor biopsies performed at Screening, at Cycle 2 (Day 8 for patients in Cohort A1), and if feasible, at the time when disease progression is suspected (especially if disease progression occurs prior to Cycle 3). Biopsies should be collected during the period between $\geq$ 2 and $\leq$ 12 hours postdose. Tumor Biopsies are optional but strongly encouraged for Cohort B patients with safely accessible soft tissue and/or visceral metastases.
15. Archival paraffin-embedded tissue may be collected to evaluate the histology of the tumor. If fresh tumor tissue biopsy cannot be obtained at screening, every reasonable effort should be made to obtain the most recent archival tissue sample. Tumor blocks are preferred, but in the event that local regulations prevent the shipment of tumor blocks, 15-20 unstained, serially cut slides are requested. Minimum tissue requirements are further described in the laboratory manual. Cytological, fine-needle aspiration, and decalcified bone biopsy samples are not acceptable.
16. Adverse Events and Concomitant Medications/Treatments: Patients must be followed for adverse events and associated concomitant medications and treatments on a monthly basis, from the first day of study treatment until at least 28 days after the last dose of study treatment, or until all serious or study drug-related toxicities have resolved or are determined to be "chronic" or "stable", whichever is later.
17. Transvaginal Ultrasound (if applicable): Assessment of endometrial thickness will be performed at Screening, at the end of treatment (if treated for at least 2 cycles), and as clinically indicated. Any abnormal bleeding should be evaluated with a complete gynecological workup.
18. Study Drug Compliance: GDC-0810 bottle(s) including any unused capsules should be brought to each clinic visit for drug accountability.

### Appendix 3 Schedule of Activities: Phase Ib Cohorts C0 and C1 (Dose Escalation)

	Screening	Cycle 1				Cycle 2		Cycle 3+ [1]	End of Treatment [2]	Safety Follow-Up (+ 2 days) [3]
Protocol Activities	≤ 28 days of 1 st dose	Day 1	Day 8 (± 1 day)	Day 15 (± 1 day)	Day 22 (± 1 day)	Day 1	Day 15 (± 1 day)	Labs CT/MRI scans		
Baseline Documentation										
Informed Consent	X									
Medical/Oncological History [4]	X									
Physical Examination [5]	X	X	X	X	X	X		X	X	(X)
CT/MRI Brain [6]	X									
Serum pregnancy test [7]	X									
Pharmacogenetic sample [8]	X									
Laboratory Studies										
Hematology and Blood Chemistry [9]	X	X	X	X	X	X	CBC only	X [1]	X	(X)
Urinalysis [9]	X							X	X	
Circulating Tumor DNA [9]	X							C3, C5	X	
Trough PK Sample [10]						X		C3, C4	X	
GDC-0810 Dosing [11]		X→	→	→	→	→	→	→		
Pa bociclib Dosing [12]		X	→	→		→	→	→		
12-Lead ECG [13]	X	X				X		As clinically indicated	X	
PK Assessment [14]		predose and at 1, 2, 3, 4, 6 hours following dosing	predose and at 1, 2, 3, 4, 6 hours following dosing							

### Appendix 3 Schedule of Activities: Phase Ib Cohorts C0 and C1 (Dose Escalation) (cont.)

Protocol Activities	Screening ≤28 days of 1 st dose	Cycle 1				Cycle 2		Labs CT/MRI scans	End of Treatment [1]	Safety Follow-Up (+ 2 days) [2]
		Day 1	Day 8 (± 1 day)	Day 15 (± 1 day)	Day 22 (± 1 day)	Day 1	Day 15 (± 1 day)			
Efficacy/PD Assessments										
CT/MRI Chest, Abdomen, Pelvis [15]	X							X		
Bone Scan [16]	X							X		
Tumor Biopsy (mandatory) [16]	X			X					X	
Archival Tissue Sample (optional) [17]	X									
Other Clinical Assessments										
ECOG and Vital Signs	X	X	X	X	X	X		X	X	(X)
Adverse Events/Con Meds and Treatments [18]	X	X	X	X	X	X		X	X	X
Transvaginal Ultrasound [19]	X							X	X	
Study Drug Compliance [20]			X	X	X	X		X	X	
For pre-/peri-menopausal patients only: LHRH agonist [21]	administration at least 4 weeks before study treatment start	Administration every 28 days								

Study assessments may be delayed or moved ahead of the window specified to accommodate holidays, vacations, and unforeseen delays.

#### Footnotes

- 1. Cycle 3+:** To be performed per institutional guidelines and/or as clinically indicated except for ECOG, physical examination, vital signs, creatinine, liver function tests, adverse events, concomitant medication, and study drug compliance should be monitored at each cycle. Patients receiving GDC-0810 in combination with palbociclib will have hematology collected at least monthly and as clinically indicated.
- 2. End of Treatment:** These assessments do not need to be completed if they have been performed within 1 week of study withdrawal (within 4 weeks for imaging studies and 3 months for the transvaginal ultrasound).
- 3. Safety Follow-Up:** Patients should be evaluated for safety up to 28 days after the last dose of study treatment. Physical examination (including ECOG and vitals), hematology, and blood chemistry should be performed as clinically indicated. Adverse events should be followed until all serious or study drug-related toxicities have resolved or are determined to be “chronic” or “stable”, whichever is later.

### **Appendix 3 Schedule of Activities: Phase Ib Cohorts C0 and C1 (Dose Escalation) (cont.)**

4. Medical/Oncological History: Includes oncologic history, demographics, history of other disease processes (active or resolved) and concomitant illnesses.
5. Physical Examination: Examination of major body systems, including known and suspected sites of disease. Height should be collected at Screening.
6. CT/MRI of the brain: To be performed as needed to rule out the presence of untreated CNS metastases.
7. Serum pregnancy test (for patients on LHRH agonists) must be performed and documented as negative within 14 days prior to Cycle 1, Day 1.
8. A pharmacogenomic sample will be collection prior to Cycle 1 Day 1. The pharmacogenomic analysis of genes that may affect the PK of GDC-0810 and circulating tumor DNA will be analyzed at specialty laboratories.
9. Samples for hematology, blood chemistry (except creatinine and liver function tests), and urinalysis will be performed per institutional guidelines and as clinically indicated . Circulating tumor DNA will be collected at screening C3, C5, and at progression and analyzed by a specialty laboratory. At Cycle 2 Day 15 collection of a complete blood count is required only. Creatinine and liver function tests should be monitored at each cycle.
10. Trough PK Sample: Samples should be obtained predose on the specified days ( patient should not take the study drug at home ). Additionally, if clinically feasible, samples should be obtained at the time of any serious and/or unusual adverse events that may be causally related to study drug.
11. GDC-0810 Dosing: GDC-0810 will be orally self-administered within 30 minutes after eating a meal (unless specified otherwise), except on clinic days, when the daily dose will be taken at the clinic, prior to any study assessment. One cycle consists of 28 days.
12. Palbociclib Dosing: Palbociclib will be orally self-administered on Days 1-21 of each cycle, except on clinic days, when the daily dose will be taken at the clinic, prior to any study assessment. One cycle consists of 28 days.
13. ECG: Single ECGs will be collected at Screening, Cycle 1 Day 1 (prior to first dose), Cycle 2 Day 1 and end of treatment visits. At other study visits they should be recorded as clinically indicated. If there is QTc interval prolongation (Grade > 1), the ECG should be over read by a cardiologist at the site for confirmation.
14. PK Assessment: Samples will be drawn relative to time of dose at 0 (predose), 1, 2, 3, 4, 6 hours , post-dose at Cycle 1 Day 1 and Cycle 1 Day 8.
15. Tumor Imaging: CT scans of the chest, abdomen and pelvis and a bone scan will be performed to assess disease status at Screening and per institutional guidelines and as clinically indicated .
16. Tumor Biopsies : Pre-, on- treatment and post-progression biopsies from the same (whenever feasible) soft tissue or visceral metastatic lesion that is safely accessible will be collected at Screening, Cycle1 Day 15, between $\geq 2$ and $\leq 12$ hours post-dose, and at the time of progression.

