### **Continuous Dosing**

In Phase Ia GDC-0810 will be given continuously beginning on Cycle 1 Day 1 in 28-day cycles. During Cycle 1 of the dose escalation, patients will return to the clinic on a weekly basis (Days 8, 15, and 22) for safety evaluation and collection of predose PK samples. On those days, treatment will be administered in the clinic.

Similarly, on Day 1 of every subsequent new cycle of dosing beginning with Cycle 2, study drug will be administered in the clinic following all the assessments as indicated in the Schedule of Activities.

All other doses of GDC-0810 will be administered on an outpatient basis. It is anticipated that some patients may occasionally forget to take a dose of GDC-0810. In those cases, patients should just take the next scheduled dose, without compensating for the missed dose.

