### **15.3.6 Ventricular Repolarization**

Standard ECG intervals RR and QT will be determined for each ECG recording. Corrected QT intervals (QTc) will be determined using Fridericia's formula. Changes in ECG intervals from baseline will be calculated. Baseline is defined as either the single ECG measurement (Phase I) or the mean of the triplicate ECG measurements (Phase II) collected during screening. Standard evaluation procedures will be employed in the reading of the ECGs.

Tables to be prepared include analysis of time-matched mean differences between baseline and postdose assessments, and analysis of maximum change from baseline for each patient.

In addition, patient's QTc (Fridericia) will be categorized based on ICH E14 guidance. Tables will present the number and percentage of patients meeting or exceeding the following categories:

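### Three dosing footnotes put the clinic-day dose ahead of samples that must be predose, and Section 15.3.2 lets a same-day post-dose laboratory value count as baseline (minor)

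*Combined protocol and SAP*

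**What the plan says.** **Dose first.** Appendix 3, footnotes 11 (GDC-0810) and 12 (palbociclib), covers Cohorts C0 and C1. Both drugs are self-administered "except on clinic days, when the daily dose will be taken at the clinic, prior to any study assessment". Appendix 1, footnote 9, makes the same exception for Phase Ia patients on clinic days, "when they will take their daily dose at the clinic, prior to any study assessment".

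**Sample first.** In Appendix 1, footnote 8 requires trough samples to be predose and adds "patient should not take the study drug at home". Footnote 11 sets the Cycle 2 profile: "Samples will be drawn relative to time of dose at 0 (predose), 0.5, 1, 1.5, 2, 3, 4, 6, 8, and 24 hours postdose". Footnote 12 does the same for Day -7. In Appendix 3, footnotes 10 and 14 require predose troughs and a time-zero sample, and footnote 13 requires an ECG at "Cycle 1 Day 1 (prior to first dose"). Section 11.4 repeats the predose PK requirement. For Day 1 of Cycle 2 onward, Section 10.3.1 says "study drug will be administered in the clinic following all the assessments as indicated in the Schedule of Activities", and Section 10.3.3 gives the same order for Phase Ib.

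**Baseline.** Section 15.1 defines baseline as the closest measurement before the first dose. Section 15.3.2 defines laboratory baseline as the last value on or before the date of the first dose, with no requirement that it precede the dose. For ECGs, Section 15.3.6 says: "Baseline is defined as either the single ECG measurement (Phase I) or the mean of the triplicate ECG measurements (Phase II) collected during screening".

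**The concern.** The footnotes and the predose rules govern the same visits and cannot both be obeyed. A site that followed the footnote would draw a post-dose sample and label it a trough. PK is the secondary objective of Phases Ia and Ib (Section 6.2), and Section 15.4 collects steady-state troughs.

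The laboratory problem concerns the analysis rule itself. The Section 15.3.2 baseline feeds the table of baseline grade against worst post-baseline grade. If that baseline was drawn after the first dose, an early drug effect is counted as a pre-existing abnormality and the shift is understated. The two problems meet on the first-dose day in Phase Ia and C0/C1, where the footnotes direct the dose first and Section 15.3.2 then accepts the resulting value.

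**Working it through.** The plan states no figure on this point to reproduce. The check compares the texts, then sizes the effect.

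**1. Can the texts be reconciled?** The only qualifier, in Appendix 3, footnote 11, allows exceptions to the meal timing, not to the order of dose and assessment. Footnote 12 and Appendix 1, footnote 9, have no qualifier. The dosing footnotes for Phase IIa (Appendix 2, footnote 9) and Cohort D1 (Appendix 4, footnote 11) omit the dose-first clause. The conflict is therefore confined to Phase Ia and C0/C1.

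**2. Size of the trough error, if the footnote was followed.** Inputs from Section 1.2: mean terminal half-life of about 8 h (after a single 600 mg non-fasted dose) and peak at 1 to 3 h. Assumptions: one compartment, first-order absorption, steady state, and dosing interval τ = 24 h.

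- ke = ln 2 / 8 = 0.0866 per h
- C(t) ∝ exp(−ke·t)/(1 − exp(−ke·τ)) − exp(−ka·t)/(1 − exp(−ka·τ))
- ka is solved so that the peak falls at 1 h (3.71 per h) or 3 h (0.771 per h).
- True trough: C(24) = 0.125/0.875 = 0.1429

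At 30 minutes with a 3 h peak: 0.9576/0.875 − 0.680 = 0.414, and 0.414/0.1429 = 2.9. At 5 minutes with a 1 h peak: 0.9928/0.875 − 0.734 = 0.400, and 0.400/0.1429 = 2.8.

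| Delay from dose to draw | Reading ÷ true trough (peak at 1 to 3 h) |
|---|---|
| 5 min | 1.4 to 2.8 |
| 30 min | 2.9 to 6.6 |
| 1 to 3 h | 4.1 to 7.2 |

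For the 1 to 3 h row, a half-life of 6 h gives 6.7 to 13.8 and 12 h gives 2.5 to 3.7. Twice-daily dosing at 8 h gives 1.6 to 2.5. Palbociclib cannot be sized, because the documents give neither its half-life nor its peak time.

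**3. How many troughs are exposed, at most.**

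- Phase Ia: Days 8, 15 and 22 in 41 patients (Section 1.1): 3 × 41 = 123. The Cycle 2 Day 1 predose sample is left out because that profile has its own 24 h sample, taken before the next dose (Section 11.4.1).
- C0/C1: Cycle 1 Day 8, Day 1 of Cycles 2, 3 and 4, and end of treatment, making 5 per patient. With 4 patients (Section 1.1) to about 5 (Section 15.2.3), this is 5 × 4 = 20 to 5 × 5 = 25.

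**4. Laboratory baseline.** Hematology and chemistry are scheduled on the first-dose date in every phase: Day -7 in Appendix 1, and Cycle 1 Day 1 in Appendices 2, 3 and 4. A same-day value drawn before the dose satisfies both Sections 15.1 and 15.3.2. They disagree only on a same-day value drawn after it. The dose-first footnotes direct that case in 41 + 4 = 45 to 41 + 5 = 46 patients.

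**The case against.** The strongest reply is that the protocol already settles the order. The trough footnotes require predose sampling and bar dosing at home. Section 11.4 repeats the requirement, Sections 10.3.1 and 10.3.3 call for predose samples on Days 8, 15 and 22 of Cycle 1, and Section 15.4 itself describes troughs as predose. On that view the footnote clause is a drafting slip, and a late sample already falls outside the definition. The Laboratory Manual, which the documents cite but do not include, may also cover it. Most of this stands, and it is why the point is minor. It does not make the three footnotes correct, and Section 15.4 does not say how a late sample is identified or handled.

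On baseline, one can say that Section 15.3.2 is the specific rule and overrides Section 15.1. That settles precedence but leaves a rule that admits an on-treatment value.

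A reader might infer more than the documents support:

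- **That the Phase Ia and Ib troughs are contaminated.** Nothing shows that any site dosed first.
- **That the bias is at least fourfold.** That holds only for a draw 1 h or more after the dose, and no delay is stated.
- **That every patient's laboratory baseline is suspect.** The Section 15.3.2 wording covers all phases, but Phase IIa and Cohort D1 carry no dose-first instruction.
- **That QTc change is affected.** Section 15.3.6 takes the ECG baseline from screening, so the ECG conflict has no effect on the analysis.
- **That Sections 10.3.1 and 10.3.3 also need correcting.** Their sentence defers to the Schedule of Activities, which gives the postdose times.

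**Conclusion.** Minor, but wrong as written on both counts. The three footnotes contradict the predose requirements in their own appendices, and Section 15.3.2 admits a baseline that Section 15.1 excludes. Confidence in the text conflict is high.

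The consequences are conditional. The trough ratios hold only if a site followed the footnote, and they rest on the one-compartment model, the 8 h half-life, once-daily dosing and an assumed delay. The counts of 123 and 20 to 25 are ceilings. The size of any laboratory shift cannot be derived from the documents. Enrollment is closed and the analyses are descriptive, with no sample size or Phase IIa activity result involved. What remains is how samples and baselines already collected are classified, plus any end-of-treatment troughs still to be drawn in Cohort C1.

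**What to change.** 1. In Appendix 1, footnote 9, and Appendix 3, footnotes 11 and 12, replace the dose-first clause with a statement that the clinic-day dose is taken after all predose assessments.
2. When troughs are summarised under Section 15.4, exclude or flag any sample whose recorded time is after that day's dose.
3. In Section 15.3.2, define laboratory baseline as the last value collected before the first dose. Drop a first-dose-day value only when its recorded time is after the dose. Where no time was recorded, keep the value and flag it, or add a sensitivity shift table using screening values. Automatic reversion to screening is not advised: it would discard valid predose values for ones up to 28 days old, against the closest-measurement rule in Section 15.1.

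The cost is a few words in three footnotes and Section 15.3.2, a handling rule for Section 15.4, and a programming check of recorded dose and sample times. A few troughs or baselines may be reclassified.
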